5.4.5. Handling of Withdrawals

The primary reason for withdrawal from this trial will be recorded on the Study Status data collection form. Subjects will be encouraged to complete the Early Termination Visit. The Early Termination Visit procedures are listed in [Section 7.5](#).

Subjects who withdraw, or are withdrawn or terminated from this trial, or are lost to follow-up after signing the ICF, randomization, and receipt of study vaccine may be replaced to ensure each vaccine arm has at least 20 evaluable subjects, up to a total of 60 evaluable subjects. In order to be evaluable, a subject must receive the ChAd3-EBO-Z vaccine at Visit 1 and the booster vaccination of either ChAd3-EBO-Z, MVA-BN®-Filo, or placebo on Day 8 as determined by randomization.

Subjects who withdraw, or are withdrawn or terminated from this trial, or are lost to follow-up after signing the ICF and randomization but before receipt of study vaccine may be replaced.

5.4.6. Termination of Study

Although the sponsor has every intention of completing this trial, it reserves the right to terminate this trial at any time for clinical or administrative reasons. Reasons for termination include, but are not limited to, study closure due to the recommendation after a SMC review and at the discretion of DMID.

If the study is prematurely terminated by the sponsor, any regulatory authority, or the investigator for any reason, the investigator will promptly inform the study subjects and assure appropriate therapy or follow-up for the subjects, as necessary. The investigator will provide a detailed written explanation of the termination to the IRB/IEC.

6 STUDY INTERVENTION/INVESTIGATIONAL PRODUCT

6.1. Study Product Description

The ChAd3-EBO-Z vaccine consists of a recombinant replication-defective chimpanzee adenovirus Type 3 vector engineered to express the WT GP antigen from EBOV. The vaccine is formulated in a buffer (without addition of a preservative). The formulation buffer, pH 7.4, is composed of 10 mM Tris, 10 mM Histidine, 5% Sucrose (w/v), 75 mM Sodium Chloride, 1 mM Magnesium Chloride, 0.02% Polysorbate 80 (PS-80) (w/v), 0.1 mM EDTA, and 0.5% Ethanol (v/v).

The MVA-BN®-Filo vaccine is based on the highly attenuated virus vector, Modified Vaccinia Ankara Bavarian Nordic (IMVAMUNE®). The recombinant vaccine encodes the glycoproteins of Ebola Virus Sudan, Ebola Virus Zaire, and Marburg Virus Musoke and the nucleoprotein of Tai Forest Ebola virus. The vaccine is manufactured in Chicken Embryo Fibroblast (CEF) cells derived from Specific Pathogen Free (SPF) eggs in a suspension culture using serum free medium.

6.1.1. Acquisition

ChAd3-EBO-Z

ChAd3-EBO-Z will be provided by GlaxoSmithKline.

MVA-BN®-Filo

MVA-BN®-Filo will be provided by Janssen Vaccines and Prevention BV in collaboration with Bavarian Nordic.

Placebo

Placebo, 0.9% Sodium Chloride Injection, USP will be provided by the DMID Clinical Materials Services, Fisher BioServices.

Upon request by DMID, MVA-BN®-Filo and ChAd3-EBO-Z will be shipped to the following address:

DMID Clinical Materials Services
Fisher BioServices
[name]
[name]
[contact]
[contact]
Email: [contact]

MVA-BN®-Filo, ChAd3-EBO-Z and placebo will be provided through the DMID Clinical Materials Services to the participating VTEU site prior to the start of this trial upon request and with prior approval from DMID. Should the site principal investigator require additional vaccine during this trial, further instructions are provided in the protocol-specific MOP.

6.1.2. Formulation, Packaging, and Labeling

ChAd3-EBO-Z

ChAd3-EBO-Z is presented as a clear, sterile liquid suspension filled in stoppered glass vials. The nominal titer for the vaccine is 2×10^{11} vp/mL. Vials have a fill volume of approximately 1.2 mL. 1.0 mL is to be administered IM.

The study product will be labeled according to manufacturer specifications and include the statement “Caution: New Drug – Limited by Federal Law to Investigational Use”.

MVA-BN®-Filo

MVA-BN®-Filo is a milky, light yellow suspension with no visible extraneous particles and contains trometamol (tris-hydroxymethyl-amino methane) and sodium chloride as formulation buffers.

The vaccine is supplied in a 2mL type I borosilicate glass vial closed with a sterile bromobutyl rubber stopper, crimped with an aluminum cap and covered with a polypropylene closure. The nominal titer for the vaccine is 2.0×10^8 Inf. U/mL. Vials are filled with an extra amount of vaccine (fill volume: 0.69 mL) to assure an extractable volume of 0.5mL.

The study product will be labeled according to manufacturer specifications and include the statement “Caution: New Drug – Limited by Federal Law to Investigational Use”.

Placebo

Placebo will be supplied as 0.9% Sodium Chloride Injection, USP which is a colorless, sterile, nonpyrogenic, isotonic solution of sodium chloride and water for injection (WFI). Each mL contains sodium chloride 9 mg. It contains no bacteriostatic, antimicrobial agent, or added buffer and is supplied only in single-dose containers. The placebo, 0.9% Sodium Chloride, contains no preservatives. The solution may contain hydrochloric acid and/or sodium hydroxide for pH adjustment (pH 5.3 [4.5 to 7.0]). 0.5 mL is to be administered IM.

6.1.3. Product Storage and Stability

ChAd3-EBO-Z

ChAd3-EBO-Z vaccine vials must be stored at -60°C to -90°C. If the vaccine cannot be administered immediately, it is recommended to administer the product within 6 hours after thawing.

MVA-BN®-Filo

MVA-BN®-Filo vaccine vials must be stored at -20°C to -80°C. If the vaccine cannot be administered immediately it is recommended to administer the product within 4 hours after preparation in syringe.

Placebo

Placebo must be stored at 20°C to 25°C (68°F to 77°F) [See USP Controlled Room Temperature; excursions between 15°C and 30°C (59°F and 86°F) are permitted]. See protocol-specific MOP for further instructions.

The temperature of the storage unit must be recorded manually daily (excluding non-business days and holidays as applicable), continuously monitored and recorded during the duration of this trial per the participating VTEU site's standard operating procedures (SOPs), and documentation will be maintained. If the temperature fluctuates outside of the required range, the affected study product(s) must be quarantined at the correct storage temperature and labeled as 'Do Not Use' (until further notice). The research pharmacist must alert the site principal investigator and study coordinator, if the temperature fluctuates outside of the required range. In the event the temperature fluctuates outside of the required range, the affected study product(s) must not be administered. The site principal investigator or responsible person should immediately contact the DMID Product Support Team at [contact] for further instructions before any additional study vaccinations are administered. Based on the information collected, DMID and/or the manufacturer will determine whether the affected study product(s) can be used. If it cannot be used, the site will receive specific instructions on how to return the affected study product(s) to the DMID CMS or destroy it on site. Additional instructions for quarantine are provided in the protocol-specific MOP.

6.2. Dosage, Preparation and Administration of Study Intervention/Investigational Product

See the protocol-specific MOP for detailed information on the preparation, labeling, storage, and administration of study product for each treatment arm. Study product preparation will be performed by the participating VTEU site's research pharmacist on the same day of study vaccine administration.

Visually inspect the study product upon receipt and prior to use. If the study product(s) appear(s) to have been damaged, contaminated or discolored, contain visible particulate matter or if there

are any concerns regarding its integrity, do NOT use the affected study product(s). The affected study product(s) must be quarantined as per storage requirements and labeled as 'Do Not Use' (until further notice). The site principal investigator or responsible person should immediately contact the DMID Product Support Team at [contact] and DMID Clinical Project Manager for further instructions before any additional study vaccinations are administered. Based on the information collected, DMID and/or the manufacturer will determine whether the affected study product(s) can be used. If it cannot be used, the site will receive specific instructions on how to return the affected study product(s) to the DMID CMS or destroy it on site. If the study product is unusable, study personnel will use another vial from the study supply. Replacement vials may be requested by contacting DMID. Additional instructions for quarantine and DMID contact information are provided in the protocol-specific MOP.

ChAd3-EBO-Z

The study product will be prepared for administration by thawing at room temperature. Once the last ice crystals have disappeared within the thawed vials, the vial should be gently shaken to homogenize the suspension. After thawing, the drug product should appear as transparent and without precipitates. The vaccine should be visually inspected for any foreign particulate matter prior to administration. In case foreign particulate matter is visible, the vaccine must not be used. The final dose of vaccine will be 2×10^{11} vp.

MVA-BN®-Filo

The study product will be prepared for administration by thawing at room temperature. To ensure homogeneity, upon thawing the vial should be swirled gently (not shaken) for at least 30 seconds. After thawing, the drug product should appear as a clear to milky colored suspension. The liquid vaccine should be visually inspected for any foreign particulate matter prior to administration. In case foreign particulate matter is visible, the vaccine must not be used. The final dose of vaccine will be 1×10^8 IU.

The vaccines will be administered via intramuscular injection into the deltoid. For the second injection, subjects will receive study vaccine or placebo via intramuscular injection into the opposite arm that was used for the first injection (left or right deltoid). Study product administration will be performed by an unblinded study personnel member who is credentialed to administer vaccines and may also participate in dose preparation, but will not be involved in study-related assessments or have subject contact for data collection following study vaccine administration.

6.3. Modification of Study Intervention/Investigational Product for a Subject

There will be no dose modifications. If a subject's second vaccination is deferred, attempts will be made to reschedule the vaccination to occur within the acceptable protocol-specified window for that visit.

6.4. Accountability Procedures for the Study Intervention/Investigational Product(s)

After receipt of the study vaccine, the site principal investigator is responsible for its distribution and disposition, and has ultimate responsibility for study vaccine accountability. As this is a blinded study, the site PI will delegate this responsibility to the unblinded site pharmacist. Study vaccine records must be maintained and document logs of receipt, accountability, and storage temperature conditions. The study product accountability records and dispensing logs will also capture vial numbers, including final vial number, date of study vaccine preparation/administration, time of study vaccine preparation, time study vaccine is drawn into the syringe, and amount of study vaccine withdrawn for administration. Time of study vaccine administration to the subject will be captured on the appropriate data collection form. All study vaccine, whether administered or not, must be documented on the appropriate study product accountability record or dispensing log. The sponsor's monitoring staff will verify the participating VTEU site's study product accountability records and dispensing logs per the site monitoring plan.

Used and unused vaccines, will be retained until monitored and released for disposition as applicable. Filled, un-used syringes will be retained until monitored and released for disposition as applicable. Final disposition of the unused vaccine will be determined by DMID and communicated to the participating VTEU site by the DMID Clinical Project Manager.

6.5. Assessment of Subject Compliance with Investigational Product

Study products will be administered to subjects via intramuscular injection by study personnel according to subject treatment assignment and as described in [Section 6.2](#) Thus, subject compliance is not anticipated to be an issue. Deviations from the dose schedule may only occur as described in [Section 6.3](#).

6.6. Concomitant Medications/Treatments

Administration of any medications, therapies, or vaccines will be recorded on the appropriate data collection form. Concomitant medications will include all current medications and medications taken within 60 days prior to signing the informed consent form through approximately 28 days after the second study vaccination or early termination (if prior to 28 days

after the second study vaccination), whichever occurs first. Assessment of study eligibility will include a review of all permitted and prohibited medications per the Subject Inclusion and Exclusion Criteria (see [Section 5](#)). Medications reported in the electronic case report form (eCRF) are limited to those taken within 30 days prior to study vaccination through approximately 28 days after the second study vaccination. Prescription and over-the-counter drugs will be included as well as herbals, vitamins, and supplements. In addition, receipt of non-study vaccines will be solicited through approximately 28 days after the second study vaccination, and reported in the eCRF.

Use of new medication should prompt evaluation for the occurrence of an AE or worsening of a pre-existing medical condition.

Medications that might interfere with the evaluation of the investigational product(s) should not be used from time of study vaccination through 28 days post the second vaccination unless clinically indicated as part of the subject's health care. Medications in this category include the prohibited medications per the Subject Exclusion Criteria (see [Section 5.2](#)). In addition, the site principal investigator or appropriate sub-investigator may identify other medications that should not be used due to a risk to subject safety or assessment of reactogenicity and immunogenicity. Use of medications as prophylaxis prior to study vaccination is prohibited. There are no known drug-vaccine interactions with the study vaccine and subjects are not being asked to discontinue current medications not listed in the exclusion criteria. In the event medical conditions dictate use of medications, subjects are encouraged to obtain adequate care, comply with the course of therapy as prescribed by their physician and inform the site as soon as practicable. Details of all medications taken during the medication reporting period for this study (date, indication, brand or generic name) will be recorded.

7 STUDY SCHEDULE

Complete study schedule details listed by type of visit are described below. Refer also to [Sections 4](#) and [8](#), and [Appendix A](#): Schedule of Study Procedures and Evaluations.

7.1. Screening

Day < - 29 to -1, Visit 00

Potential subjects will be screened for eligibility within 28 days prior to the administration of study vaccination. The following activities will be performed at screening and may be done all at one visit or split into separate visits:

- Subjects will be provided with a description of this trial (purpose and study procedures) and asked to read and sign the informed consent form. The informed consent form will be signed prior to performing any study procedures, including any screening procedures.
- Demographic information will be obtained by interview of subjects.
- History of military service prior to 1991 or after January 2003. Subjects will be interviewed for possible receipt of vaccinia-based vaccine.
- Eligibility criteria will be reviewed with subjects.
- Complete medical history will be obtained by interview of subjects.
- History of all concomitant medications taken within 60 days prior to signing the informed consent form will be reviewed with subjects. Medications reported in the eCRF are limited to those taken within 30 days prior to study vaccination. Assessment of study eligibility will include a review of all permitted and prohibited medications per the Subject Inclusion and Exclusion Criteria (see [Section 5](#)).
- Vital signs, including oral temperature, pulse, and blood pressure, will be obtained. Subjects must not eat or drink anything hot or cold, or smoke within 10 minutes prior to taking oral temperature.
- Height and weight will be collected. BMI will be calculated to determine eligibility.
- An ECG will be performed and read to determine eligibility.
- A physical examination will be performed to include the following organs and organ systems: general appearance, skin, head and neck, lungs, heart, liver, spleen, extremities, musculoskeletal, lymph nodes, and nervous system by a study clinician licensed to make medical diagnoses and listed on the Form FDA 1572 as the site principal investigator or sub-investigator.

- A serum pregnancy test will be performed on all females of childbearing potential and must be negative.
- Venous blood will be collected for screening laboratory tests (refer to [Section 8.2.1](#)) to be run at the local clinical laboratory.
- Urine will be collected for screening urinalysis (dipstick) for urine protein and urine toxicology screen for opiates. Values must meet the eligibility criteria (see [Section 5](#)) prior to randomization.

7.2. Enrollment/Baseline

Day 1, Visit 1

Sixty subjects who meet all inclusion and no exclusion criteria will be administered study product. The following procedures will occur for all Treatment Arms:

- Subject's willingness to participate will be reconfirmed and documented in the subject's study records prior to performing any further study procedures, including administration of the study vaccine.
- Eligibility criteria, including results of all clinical screening laboratory evaluations, will be reviewed with subjects prior to study vaccination to ensure continued eligibility.
- Complete medical history and any updates obtained by interview of subjects since the screening visit will be reviewed with subjects prior to study vaccination to ensure continued eligibility.
- All concomitant medications will be reviewed with subjects prior to study vaccination for accuracy and completeness. Any new concomitant medications (including non-study vaccines) taken since the screening visit will be reviewed with subjects and assessed for continued eligibility prior to study vaccination. Medications reported in the eCRF are limited to those taken within 30 days prior to study vaccination.
- Vital signs, including oral temperature, pulse, and blood pressure, will be obtained to ensure eligibility. Vital signs assessed on Day 1 prior to the first study vaccination will be considered as baseline. Subjects must not eat or drink anything hot or cold, or smoke within 10 minutes prior to taking oral temperature.
- A targeted physical examination may be performed prior to study vaccination, if indicated based on review of complete medical history and any updates obtained by interview of subjects since the screening visit, by a study clinician licensed to make medical diagnoses and listed on the Form FDA 1572 as the site principal investigator or sub-investigator.

- A urine pregnancy test will be performed within 24 hours prior to study vaccination on all females of childbearing potential. Results must be negative and known prior to randomization and study vaccination.
- Subjects will be enrolled in AdvantageEDCSM and assigned randomly to a treatment arm prior to study vaccination.
- Venous blood will be collected prior to the study vaccination for safety labs (refer to [Section 8.2.1](#)).
- Venous blood will be collected prior to the study vaccination for high resolution HLA typing for Class 1 (A, B, and C locus) testing.
- Venous blood will be collected prior to the study vaccination for future use assays.
- Venous blood will be collected prior to the study vaccination for baseline immunogenicity and exploratory assays (please refer to [Appendix A](#): Schedule of Study Procedures and Evaluations for type of assays requiring collection).
- Pre-administration reactogenicity assessments will be performed prior to study vaccination to establish a baseline. Subjects will then receive study vaccine or placebo via intramuscular injection into the left or right deltoid. The time of administration will be recorded on the appropriate data collection form. Subjects will be observed for at least 30 minutes after study vaccination. Post-administration reactogenicity assessments will be performed. Any AE/SAEs/MAAEs will be recorded on the appropriate data collection form prior to discharge from the clinic.
- Subjects will be provided with a memory aid and other study-related materials to record daily oral temperature, solicited site and systemic AEs, unsolicited AEs, and concomitant medications. Subjects will be encouraged to take their oral temperature around the same time each day. Subjects must not eat or drink anything hot or cold, or smoke within 10 minutes prior to taking oral temperature. Subjects will be instructed on how to use their memory aid and how to measure and record AEs prior to discharge from the clinic. Subjects will be instructed to notify the study center if they develop any severe reactions after study vaccination. If the site principal investigator or appropriate sub-investigator deems the reaction severe enough, further instructions will be given to the subject on the proper course of action, including a return to the clinic for immediate evaluation if appropriate.

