Fever within 7 days post-vaccination was observed in 5% of the subjects in the control group, in none of the subjects who received the 1×10^{10} pu dose, in 14.2% of the subjects who received 2.5×10^{10} pu, in 19.2% of the subjects who received 5×10^{10} pu and in 38.1% of the subjects in the 1×10^{11} pu groups. The only Grade 3 fever occurred with 5×10^{10} pu in the study ChAd3-EBOZ Lau. The onset of fever was mostly on Day 0-1 (except for 6 cases on Day 3-6) and fever was mostly self-limiting within 1 day. There was a clear dose-dependent increase in fever (any grade).

Transient non-clinically significant lymphopenia, neutropenia and anemia were observed within the first 28 days post vaccination with all doses (except neutropenia with 1×10^{11} pu) across all trials (including lymphopenia and neutropenia in the placebo control group in the study ChAd3-EBOZ Lau [only trial with a placebo control group]). The majority of these events were Grade 1. There is no evidence suggesting that the magnitude of these non-clinically significant changes increases with increasing vaccine dose.

Seven cases of transient platelet count drops met as per protocol criteria for thrombocytopenia ($<150 \times 10^9/L$), 4 in subjects who received 2.5×10^{10} pu and 3 in subjects who received 5×10^{10} pu. No clinical signs or symptoms suggestive of increased tendency for bleeding were reported. No thrombocytopenia was reported with 1×10^{10} and 1×10^{11} pu. Transient non-clinically significant drops in platelet count within 7 and within 28 days post-vaccination not meeting criteria for thrombocytopenia seem to be induced by vaccination ('real' phenomenon) i.e. seen consistently across trials and seen less frequently with in the placebo group included in the study ChAd3-EBOZ Lau.

No significant related unsolicited AEs were reported with any of the doses in any of the trials. No Suspected Unexpected Serious Adverse Reactions were reported. The only SAE reported to date (peritoneal tuberculosis 14 days post vaccination) is considered unrelated to vaccination.

Safety in Phase II Studies:

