9.3. Adverse Events

9.3.1. Solicited Events and Symptoms

Solicited adverse events collected 30 minutes post-vaccination (in-clinic assessment) and then daily for 7 days after each vaccination (through Day 8) will be graded on a scale of 0 (absent), 1 (mild), 2 (moderate) and 3 (severe). Local reactogenicity grading are provided in [Table 4](#) and [Table 5](#) and include:

- Pain – experienced without touching the injection site (spontaneous discomfort)
- Tenderness – hurts only when injection site is touched, or the arm is moved
- Erythema (Redness)
- Induration (Hardness/Swelling)
- Ecchymosis (Bruising)
- Pruritus (Itching)

The systemic reactogenicity grading is provided in [Table 6](#) and [Table 7](#) and includes:

- Feverishness (chills/shivering/sweating)
- Malaise (General Unwell Feeling)

- Fatigue (Tiredness)
- Myalgia (Body Aches/Muscular Pain)
- Headache
- Nausea
- Loss of Appetite
- Elevated Oral Temperature

Pre-second dose, safety events will include all safety assessments through Day 8 post-dose 1. If the second dose occurred on Day 8, Day 8 pre-second dose safety events will include memory aid assessments and in-clinical assessments that occurred prior to dose 2.

Safety data will be summarized for the Safety Analysis Population. Pre-second vaccination, Study Groups 1, 2, 3 will be analyzed jointly as one study group as all three groups received the same vaccine at Day 1.

[Table 23](#) will provide an overview of safety events by study arm and overall. Solicited AEs will be summarized using the maximum severity over all days after each vaccination overall by vaccination and symptom (subjects with mild or higher severity grading, [Table 24](#)) and by severity (none, mild, moderate, severe) and symptom ([Table 25](#)). In both cases, the resulting number, percentage (observed rate) of subjects and associated exact (Clopper-Pearson) 95% CIs by symptom, any systemic symptom, any local symptom, and any symptom (systematic or local symptom) will be provided. In addition, solicited AEs will be tabulated by severity for each day after each study vaccination (Days 1 through Day 8) following each vaccination ([Table 26](#) and [Figure 4](#)). Subject-level solicited events will be provided as shown in [Listing 10](#) and [Listing 11](#).

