9.7. Vital Signs and Physical Evaluations

Vital sign severity grading criteria can be found in [Table 8](#). Vital sign measurements included oral temperature, systolic and diastolic blood pressure and heart rate assessed at Screening, Days 1 and 8. Vital signs will be tabulated by maximum severity grade (none, mild, moderate, severe) and study day, for each treatment group separately, overall and by vital sign variable ([Table 38](#)). Individual data listings of vital signs and physical exam findings will be provided in [Listing 15](#) and [Listing 16](#), respectively.

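### A once-daily temperature at about the same hour, with no prompt to measure when feverish, may understate fever frequency and grade

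*Protocol*

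**What the plan says.** At both vaccination visits subjects receive a "memory aid and other study-related materials to record daily oral temperature" (Protocol 7.2, repeated in 7.3.2). The only timing advice is "Subjects will be encouraged to take their oral temperature around the same time each day". SAP 9.3.1 describes the same frequency: "Solicited adverse events collected 30 minutes post-vaccination (in-clinic assessment) and then daily for 7 days after each vaccination".

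Scheduled clinic temperatures are few. SAP 9.7 states: "Vital sign measurements included oral temperature, systolic and diastolic blood pressure and heart rate assessed at Screening, Days 1 and 8". Protocol Appendix A marks the Day 1 and Day 8 measurements as taken before vaccination. Subjects also attend on Days 2, 3, 4, 6 and 9, but no routine vital signs are listed for those visits.

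Protocol 2.3.1 describes fever in the Phase 1 trials of this vaccine: "The onset of fever was mostly on Day 0-1 (except for 6 cases on Day 3-6) and fever was mostly self-limiting within 1 day". In the 1×10^11 pu groups, fever within 7 days occurred in "38.1% of the subjects". The same section equates that dose with the 2×10^11 vp given here.

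Fever is graded by Protocol Table 6 (37.8-38.4, 38.5-38.9 and above 38.9 °C). It has its own rows, Elevated Oral Temperature, in SAP Tables 24 to 26.

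**The concern.** Frequency and severity of solicited systemic reactions is a primary outcome (Protocol 3.2.1). The expected fever is common, early and brief, and is sampled about once every 24 hours. A subject who is febrile overnight but reads at noon could record nothing, or a value below the peak. The SAP takes the maximum severity over what was reported, which cannot recover a peak nobody measured. At stake are the absolute fever rate and its grade distribution, which matter in a trial whose stated purpose is preliminary estimates of safety (Protocol 11.1).

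**Working it through.** The plan gives no power, precision or detection figure for fever, so there is nothing to reproduce. The 38.1% cannot be rebuilt either, because counts are not given (8/21 and 16/42 both fit). What follows is a sensitivity range.

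**Inputs.**
- From the documents: one reading per 24 h; 60 subjects pooled after Dose 1; fever rate 38.1% at this dose; Table 6 cut-offs.
- Assumed: D, the hours above 37.8 °C; a reading hour random relative to the fever; 38.1% as the true rate.

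**Detection.** P(caught) = min(1, D/24). Expected observed rate = 38.1% × P. Expected count = 60 × 0.381 × P.

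| D (h) | P(caught) | Observed rate | Expected count of 60 |
|---|---|---|---|
| 6 | 25% | 9.5% | 5.7 |
| 12 | 50% | 19.1% | 11.4 |
| 18 | 75% | 28.6% | 17.1 |
| 24 | 100% | 38.1% | 22.9 |

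**Against sampling error.** The exact 95% interval for 23/60 is 26.1-51.8%; for 11/60 it is 9.5-30.4%. At 12 h the second interval excludes 38.1%, so the loss can exceed sampling error. At 24 h there is no loss.

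**Grade.** Assume a half-sine curve from 37.0 °C to a 38.7 °C peak (a true Grade 2), lasting L hours from start to finish, with readings rounded to 0.1 °C. The chance that one reading is at or above a cut-off c is

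(L/24) × [1 − (2/π) × arcsin((c − 37.0)/(38.7 − 37.0))],

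with c = 37.75 for any fever and 38.45 for Grade 2 after rounding.
- L = 24 h: any fever 71%, Grade 2 recorded 35%.
- L = 12 h: any fever 35%, Grade 2 recorded 17%.

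**Other sources of a temperature.**
- The 30-minute in-clinic check is early for a Day 0-1 onset.
- The Day 8 pre-dose value comes a week after Dose 1.
- Nothing is scheduled on Day 2 after Dose 1, or on Day 9 (Day 2 after Dose 2).

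**Arms.** If the same capture fraction P applies in each arm, each rate is multiplied by P. A true difference p2 − p1 then appears as P × (p2 − p1): it shrinks but keeps its direction.

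**The case against.** The case on the other side is substantial, and several parts stand.

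- **Timing is only encouraged.** A reader might infer a mandatory fixed hour. The text says about the same time and forbids no further reading. Subjects are also trained to measure and record events, and the memory aid and Manual of Procedures are not in the documents. They may already ask for more. What stands is that the two documents themselves give no such instruction.
- **Loss is not proved.** A reader might infer that short fevers are missed as a matter of fact. Duration is given only as "fever was mostly self-limiting within 1 day", never in hours. If onset clusters after a timed injection, capture depends on the reading hour and may be better or worse than D/24.
- **Grade 3.** A reader might infer that severe fevers would mostly be lost. Protocol 2.3.1 reports no Grade 3 systemic solicited event at 1×10^11 pu and a single Grade 3 fever, at 5×10^10 pu. An illustration built on Grade 3 peaks has no footing in those data.
- **Dose dependence.** The protocol calls fever dose-dependent, but only one ChAd3 dose level is used here and no dose comparison is planned.
- **Halting.** Protocol 9.5 requires the same related Grade 3 systemic event in two or more subjects, not resolved or reduced within 2 days. A fever that ends within a day would not meet it.
- **Safeguards.** Feverishness and malaise are solicited without a thermometer and feed the any-systemic-symptom rows. Memory aids are reviewed at clinic visits, and subjects are told to report severe reactions. These protect the composite but cannot supply a Table 6 temperature grade.
- **Standardisation.** Same-time readings make days and subjects comparable, whereas symptom-prompted readings vary with how the subject feels. Keeping the daily reading and adding to it meets most of this.

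**Conclusion.** The point holds as a risk of under-recording. As written, the plan may understate the frequency and grade of Elevated Oral Temperature in all arms. Under random timing, the share of fevers missed runs from none at 24 h to 75% at 6 h, with half missed at 12 h. These figures rest on assumed durations, and on treating 38.1% as true although the reading frequency behind it is not stated.

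The documents do not support a claim of bias favouring one arm: the instruction is identical in randomised, blinded arms, so contrasts are blunted unless fever duration differs by boost, which is not reported. Nor do they support a claim that the halting rule is compromised. This is a cheap improvement to a primary measurement; the endpoint is not invalid without it.

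**What to change.** In Protocol 7.2 and 7.3.2, keep the same-time daily reading and add: *and additionally whenever feverish, chilled or unwell; record the highest value of the day*. State in SAP 9.3.1 that Protocol Table 6 (SAP Table 7) is applied to that daily maximum. Optionally, record an oral temperature at the existing Day 2 and Day 9 visits.

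The cost is memory-aid wording and a short instruction to subjects, with no extra visit or blood. The downside is that fever rates will be somewhat higher and less comparable with studies that used one daily reading.

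SAP 4.3 describes enrolment in the past tense. If collection is already complete, the CSR should say that once-daily readings may understate fever frequency and grade, and should show Elevated Oral Temperature beside Feverishness.
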